## Appendix 5 - Adrenal Insufficiency Checklist

*This questionnaire should be used to determine if symptoms of **under or over replacement of glucocorticoids** have occurred in the preceding 4 weeks. Symptoms unrelated to CAH, but due to other causes, e.g. nausea with migraine, should be recorded on the eCRF AE page.*

Date of assessment (mm/dd/yyyy):				
Please ask subject:		Have you experienced any of the following symptoms more than once per week in the last 4 weeks?		
Symptoms	Yes	If Yes, do you believe this to be related to under or over replacement of glucocorticoid? Please state over/under.	No	Any clinically significant findings? Y/N
Sudden weight loss				
Sudden weight gain				
Lack of appetite				
Increased appetite				
Nausea				
Vomiting				
Headache				
Blurred vision				
Fatigue				
Weakness				
Dizziness				
Lightheadedness				
Syncope (sudden loss of consciousness)				
Sleeping difficulties				
Increased acne				
Other				
If yes to Other please specify:				

Version FINAL 1.0 – 01 Sept 2015

## Appendix 6 - SF-36®

### SF-36v2® HEALTH SURVEY (FOUR-WEEK RECALL)

#### SCRIPT FOR INTERVIEW ADMINISTRATION

**These first questions are about your health now and your current daily activities.**

**Please try to answer every question as accurately as you can.**

1. **In general, would you say your health is...** *[READ RESPONSE CHOICES]*  
*(Circle one number)*
- Excellent ..... 1  
Very good..... 2  
Good..... 3  
Fair ..... 4  
or Poor..... 5
2. **Compared to one year ago, how would you rate your health in general now?  
Would you say it is...** *[READ RESPONSE CHOICES]*  
*(Circle one number)*
- Much better now than one year ago ..... 1  
Somewhat better now than one year ago ..... 2  
About the same as one year ago..... 3  
Somewhat worse now than one year ago ..... 4  
or Much worse now than one year ago..... 5

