Urine samples will be tested for the following;

- Pregnancy test in females of childbearing potential (this test will be done locally at the site)
- Protein, glucose, specific gravity, ketones, urobilinogen, bilirubin, pH, blood

- **DEXA scans (except Germany)**  
To be performed up to 2 weeks prior to the baseline visit (Visit 1) and again within 2 weeks of Visit 4. The DEXA scans will be performed according to the site's standard clinical procedures.
- **Quality of life questionnaires (QoL)**  
QOL questionnaires (MAF, SF-36® and EQ-5D™) will be administered after breakfast on the day when the subject is not fasted and completed in a quiet environment. To be administered at baseline and Visit 4.
- **Waist circumference, height and weight**  
Waist circumference, height and weight will be measured according to each site's normal clinical practice and the result recorded in the eCRF. The subject's BMI will be calculated and recorded in the eCRF.
- **ECG**  
ECG will be performed and reported locally, and the result recorded in the eCRF.
- **Physical examination**  
A full physical examination to assess the subject's general appearance and overall health will be carried out at screening and at the last visit in the study. Significant findings that are present **prior to** the start of study drug must be included in the relevant medical history/current medical status section of the eCRF and significant findings made **after** the start of study drug which meet the definition of an AE must be recorded in the eCRF. At the other visits, an abbreviated physical examination will be conducted if indicated by AEs, noting any changes from the screening assessment. Any abnormal findings will be recorded on the eCRF.

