#### ***14.6 Case Report Forms and QoL questionnaires***

All data will be collected using an eCRF, which will automatically enter the data into a validated computerised clinical data management system.

Each subject will complete the QoL Questionnaires during the clinic visits (visits 1 and 4). The answers to the questionnaires will then be transcribed into the eCRF by the study site staff.

Laboratory data received electronically from the central laboratory will be merged with the database and not entered from the eCRF.

Analysis of the data will only be performed after all queries have been resolved using appropriate software for analysis.

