**The following three questions ask about your emotions and your daily activities.**

5a. **During the past four weeks, how much of the time have you had to cut down the amount of time you spent on work or regular daily activities as a result of any emotional problems, such as feeling depressed or anxious?** *[READ RESPONSE CHOICES]*

*(Circle one number)*

- All of the time ..... 1
- Most of the time ..... 2
- Some of the time ..... 3
- A little of the time ..... 4
- or None of the time..... 5

5b. **During the past four weeks, how much of the time have you accomplished less than you would like as a result of any emotional problems, such as feeling depressed or anxious?** *[READ RESPONSE CHOICES]*  
*(Circle one number)*

- All of the time ..... 1
- Most of the time ..... 2
- Some of the time ..... 3
- A little of the time ..... 4
- or None of the time..... 5

5c. **During the past four weeks, how much of the time did you do work or other regular daily activities less carefully than usual as a result of any emotional problems, such as feeling depressed or anxious?** *[READ RESPONSE CHOICES]*  
*(Circle one number)*

- All of the time ..... 1
- Most of the time ..... 2
- Some of the time ..... 3
- A little of the time ..... 4
- or None of the time..... 5

6. **During the past four weeks, to what extent has your physical health or emotional problems interfered with your normal social activities with family, friends, neighbors, or groups? Has it interfered . . .** *[READ RESPONSE CHOICES]*  
*(Circle one number)*

- Not at all ..... 1
- Slightly ..... 2
- Moderately ..... 3
- Quite a bit ..... 4
- or Extremely ..... 5

7. **During the past four weeks, how much did pain interfere with your normal work, including both work outside the home and housework? Did it interfere . . .** *[READ RESPONSE CHOICES]*  
*(Circle one number)*

- Not at all ..... 1
- A little bit ..... 2
- Moderately ..... 3
- Quite a bit ..... 4
- or Extremely ..... 5

8. **How much bodily pain have you had during the past four weeks? Have you had . .**  
*[READ RESPONSE CHOICES]*

*(Circle one number)*

- None..... 1
- Very mild..... 2
- Mild..... 3
- Moderate..... 4
- Severe..... 5
- or Very severe ..... 6

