**DO NOT read the following text to the survey respondent**

**Important Instruction for Interviewer:**

When using this script for interview administration of the SF-36v2 survey, note that items 7 and 8 from the Bodily Pain health domain scale are administered in reverse order from the way they appear on the printed SF-36v2 self-administered paper form. Reversing the order of the presentation of these two items facilitates the flow of the interview administration.

When recording responses from interview administration of the SF-36v2, the response to Item 7 from the interview script should be entered in the Item 8 response area on the paper form, and vice versa.

Note: All QualityMetric scoring solutions only support the scoring of items as ordered on the printed SF-36v2 self-administered paper form.

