#### **SF-36®**

The SF-36® questionnaire is a multipurpose, generic, short-form health survey containing 36 questions (4-week recall) yielding 8 health domain scales and 2 psychometrically based physical and mental component summary measures (Maruish 2011). For each questionnaire, standardised scores will be generated using a validated scoring software package (QualityMetric Health Outcomes™ Scoring Software 4.5) to calculate scores for for the 8 health domain scales and 2 summary measures using algorithms specific to the questionnaire.

The two summary measures are referred to as the physical component score and mental component score.

The 8 health domain scales to be summarised are:

- Physical Functioning (PF)
- Role-Physical (RP)
- Bodily Pain (BP)
- General Health (GH)

- Vitality (VT)
- Social Functioning (SF)
- Role-Emotional (RE)
- Mental Health (MH)

For each summary measure and scale, the change from baseline and percentage change from baseline at week 24 will be calculated. Summary statistics for absolute values at each visit, change and percentage change from baseline at week 24 will be tabulated by treatment group and pre-baseline standard therapy.

Individual question scores, summary measure scores and scale scores will be listed.

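### The SF-36 is meant to be completed by the subject, but the protocol appends the interviewer script, whose reversed pain items are not remapped for the eCRF or the scoring

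*Protocol*

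**What the plan says.** On completion, Protocol 14.6 states: "Each subject will complete the QoL Questionnaires during the clinic visits (visits 1 and 4". It continues: "The answers to the questionnaires will then be transcribed into the eCRF by the study site staff". Protocol 11.2 says only that the questionnaires "will be administered after breakfast on the day when the subject is not fasted and completed in a quiet environment", which names no interviewer and does not settle the mode.

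The instrument in Appendix 6 is the SF-36v2, four-week recall, headed "SCRIPT FOR INTERVIEW ADMINISTRATION". It carries prompts for a person reading aloud. The note to the interviewer at its end says that the two Bodily Pain items run in the reverse of the printed order. It gives the remedy: "the response to Item 7 from the interview script should be entered in the Item 8 response area on the paper form", and the other answer likewise. It then gives the reason: "All QualityMetric scoring solutions only support the scoring of items as ordered on the printed SF-36v2 self-administered paper form".

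SAP 10.7.3 says that "standardised scores will be generated using a validated scoring software package", naming the QualityMetric product, for eight domains and two component summaries. It does not mention the mode of administration, the order of items 7 and 8, or a range check.

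**The concern.** The completion procedure and the appended form do not match, and each way of resolving the mismatch in practice carries a risk.

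- If subjects fill in the script themselves, or staff key its answers by item number, the pain-interference answer goes where the software expects pain severity, and the reverse. The exchange instruction is addressed to an interviewer recording on the paper form. A subject, or someone transcribing into the eCRF, has no evident reason to apply it.
- If staff read the script aloud, they are site staff in an open-label trial (Protocol 8 and 10.1) and may know the subject's arm. Protocol 8 defends the open design partly because the primary endpoint is an objective biochemical measure. That defence does not extend to a patient-reported outcome. Sites could also differ in mode, and the plan does not record which was used.

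At stake are the Bodily Pain domain and any summary that uses it, at baseline and week 24, in both arms.

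**Working it through.** The plan states no figure on this point, so none can be reproduced. The check compares the sections and then sizes the item exchange under a stated assumption.

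**Sections side by side**

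1. Mode. Protocol 14.6 has the subject complete the form; Appendix 6 supplies an interviewer's script; Protocol 11.2 fits either. The SAP calls the MAF self-administered and the EQ-5D in Appendix 8 asks the subject to tick boxes, but no equivalent statement is made for the SF-36.
2. Item order. Script item 7 ("During the past four weeks, how much did pain interfere with your normal work") has 5 response levels, coded 1 to 5. Script item 8, on severity of bodily pain, has 6 levels, coded 1 to 6. On the printed form the two positions are reversed.
3. Data route. Protocol 14.6 goes from questionnaire to eCRF. The exchange in Appendix 6 applies to recording on a paper form. The documents do not say whether the eCRF follows script or printed order.
4. Scoring. SAP 10.7.3 uses software from the supplier that Appendix 6 says supports only the printed order, and specifies no remapping.

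**Size of an uncorrected exchange**

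Assumption: each item is scaled linearly to 0–100, higher is better, and the two are averaged with equal weight. The documents do not give the scoring algorithm, so this is an illustration only.

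Let a be the code for script item 7 (interference, 1–5) and b the code for script item 8 (severity, 1–6).

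- Exchange made: S = 50 × [(5 − a)/4 + (6 − b)/5]
- Exchange not made: S′ = 50 × [(6 − a)/5 + (5 − b)/4]
- Error: S′ − S = 50 × [(a − 1) − (b − 1)]/20 = 2.5 × (a − b)

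Results:

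- a = 3, b = 4 (moderate interference, moderate pain): S = 50 × (0.50 + 0.40) = 45.0; S′ = 50 × (0.60 + 0.25) = 42.5; error −2.5.
- a = 1, b = 5: S = 60, S′ = 50, error −10.
- a = 5, b = 1: S = 50, S′ = 60, error +10.

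There are 5 × 6 = 30 possible answer pairs. In 5 (b = 6) the value is out of range for the 5-level field. In 5 (a = b) the error is zero. In the other 30 − 5 − 5 = 20 the score is wrong with no visible sign. These are counts of possible pairs, not probabilities.

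For change from baseline with no exchange at either visit, the error is 2.5 × [(a − b) at week 24 − (a − b) at baseline]. It cancels if the gap between the two codes is the same at both visits. It does not generally cancel if the exchange is made at one visit and missed at the other.

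**The case against.** The strongest reply is that Appendix 6 contains its own safeguard. If the instruction is followed, the scoring error is zero. Protocol 14.6 presupposes a completed source document, and the printed form may be that document. To complete a questionnaire can include answering it at interview, so the sections are ambiguous rather than flatly contradictory. All of this stands. A reader might infer that the plan necessarily leads either to staff-influenced answers or to a wrong Bodily Pain score. The documents do not support that: both are possibilities that depend on site practice and an eCRF layout that the documents do not describe.

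Three further objections also stand. Subjects know their arm however the form is given, so self-completion removes only the interviewer's contribution, whose size is unknown. Nothing suggests that item order would be handled differently by arm, so no directional bias between arms is shown. Exchanging the items for every script record would itself introduce the error wherever the interviewer had already made the exchange.

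The objections do not remove the gap. The instruction is aimed at one mode and one recording document, and the plan commits to neither. The SAP lists individual question scores, but a listing is not a check, and only a severity code of 6 would look out of place.

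**Conclusion.** The inconsistency is real and minor. The mode of SF-36 administration is not settled, the appended form does not match Protocol 14.6 on its plain reading, and the item 7/8 exchange is not carried into the eCRF or the SAP. Bodily Pain may therefore be mis-scored, by up to 10 points either way on a 0–100 scale under the assumed linear scoring, and by nothing where the exchange was made.

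A reader might go further and infer that the physical and mental component scores are corrupted, or that all SF-36 records are affected. Neither can be derived. The weights behind the component scores are not given, so the statement has to stop at Bodily Pain and any summary that uses it. The number of records taken from the script, and how they were entered, is not reported.

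The SF-36 supports an exploratory objective (Protocol 6.3), and SAP 10.7.3 plans only summary statistics by treatment group and pre-baseline therapy. The primary 17-OHP analysis is untouched.

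**What to change.** **Form and mode.** Replace Appendix 6 with the printed self-administered SF-36v2. State in Protocol 11.2 and 14.6 that subjects complete it themselves at both visits, with a documented exception for those who cannot. This removes both the item-order hazard and avoidable interviewing by staff who may know the arm.

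**Records already taken with the script.** SAP 9.3.3 (version 4.0) describes the Data Review Meeting in the past tense, so this part may matter most. Add to SAP 10.7.3:

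- record for each questionnaire the mode of administration and how items 7 and 8 were entered;
- exchange the two items before scoring only where the Appendix 6 exchange was not already made;
- flag any value of 6 in the 5-level interference item. This check catches only the most severe pain answer, so it supplements the entry record and cannot replace it.

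**Cost.** One appendix, two sentences in the protocol, one conditional derivation rule and one edit check, plus the work of establishing from sites how existing records were entered. The small downside is the exception needed for subjects unable to complete the form unaided.

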**Now I'm going to read a list of activities that you might do during a typical day.**

**As I read each item, please tell me if your health now limits you a lot, limits you a little, or does not limit you at all in these activities.**

- 3a. **First, vigorous activities, such as running, lifting heavy objects, participating in strenuous sports. Does your health now limit you a lot, limit you a little, or not limit you at all?** *[READ RESPONSE CHOICES ONLY IF NECESSARY]*
- [IF RESPONDENT SAYS S/HE DOES NOT DO ACTIVITY, PROBE: Is that because of your health?]*  
*(Circle one number)*
- Yes, limited a lot ..... 1  
Yes, limited a little ..... 2  
No, not limited at all..... 3

3b. . . . moderate activities, such as moving a table, pushing a vacuum cleaner, bowling, or playing golf. Does your health now limit you a lot, limit you a little, or not limit you at all? *[READ RESPONSE CHOICES ONLY IF NECESSARY]*

*[IF RESPONDENT SAYS S/HE DOES NOT DO ACTIVITY, PROBE: Is that because of your health?]*

*(Circle one number)*

- Yes, limited a lot ..... 1
- Yes, limited a little ..... 2
- No, not limited at all..... 3

3c. . . . lifting or carrying groceries. Does your health now limit you a lot, limit you a little, or not limit you at all? *[READ RESPONSE CHOICES ONLY IF NECESSARY]*

*[IF RESPONDENT SAYS S/HE DOES NOT DO ACTIVITY, PROBE: Is that because of your health?]*

*(Circle one number)*

- Yes, limited a lot ..... 1
- Yes, limited a little ..... 2
- No, not limited at all..... 3

3d . . . . climbing several flights of stairs. Does your health now limit you a lot, limit you a little, or not limit you at all? *[READ RESPONSE CHOICES ONLY IF NECESSARY]*

*[IF RESPONDENT SAYS S/HE DOES NOT DO ACTIVITY, PROBE: Is that because of your health?]*

*(Circle one number)*

- Yes, limited a lot ..... 1
- Yes, limited a little ..... 2
- No, not limited at all..... 3

3e. . . . climbing one flight of stairs. Does your health now limit you a lot, limit you a little, or not limit you at all? *[READ RESPONSE CHOICES ONLY IF NECESSARY]*

*[IF RESPONDENT SAYS S/HE DOES NOT DO ACTIVITY, PROBE: Is that because of your health?]*

*(Circle one number)*

- Yes, limited a lot ..... 1
- Yes, limited a little ..... 2
- No, not limited at all..... 3

3f . . . **bending, kneeling, or stooping. Does your health now limit you a lot, limit you a little, or not limit you at all?** [READ RESPONSE CHOICES ONLY IF NECESSARY]

[IF RESPONDENT SAYS S/HE DOES NOT DO ACTIVITY, PROBE: Is that because of your health?]

(Circle one number)

- Yes, limited a lot ..... 1
- Yes, limited a little ..... 2
- No, not limited at all..... 3

3g. . . . **walking more than a mile. Does your health now limit you a lot, limit you a little, or not limit you at all?** [READ RESPONSE CHOICES ONLY IF NECESSARY]

[IF RESPONDENT SAYS S/HE DOES NOT DO ACTIVITY, PROBE: Is that because of your health?]

(Circle one number)

- Yes, limited a lot ..... 1
- Yes, limited a little ..... 2
- No, not limited at all..... 3

3h . . . **walking several hundred yards. Does your health now limit you a lot, limit you a little, or not limit you at all?** [READ RESPONSE CHOICES ONLY IF NECESSARY]

[IF RESPONDENT SAYS S/HE DOES NOT DO ACTIVITY, PROBE: Is that because of your health?]

(Circle one number)

- Yes, limited a lot ..... 1
- Yes, limited a little ..... 2
- No, not limited at all..... 3

3i . . . **walking one hundred yards. Does your health now limit you a lot, limit you a little, or not limit you at all?** [READ RESPONSE CHOICES ONLY IF NECESSARY]

[IF RESPONDENT SAYS S/HE DOES NOT DO ACTIVITY, PROBE: Is that because of your health?]

(Circle one number)

- Yes, limited a lot ..... 1
- Yes, limited a little ..... 2
- No, not limited at all..... 3

3j. . . . **bathing or dressing yourself. Does your health now limit you a lot, limit you a little, or not limit you at all?** *[READ RESPONSE CHOICES ONLY IF NECESSARY]*

*[IF RESPONDENT SAYS S/HE DOES NOT DO ACTIVITY, PROBE: Is that because of your health?]*

*(Circle one number)*

- Yes, limited a lot ..... 1
- Yes, limited a little ..... 2
- No, not limited at all..... 3

**The following four questions ask you about your physical health and your daily activities.**

4a. **During the past four weeks, how much of the time have you had to cut down on the amount of time you spent on work or other daily activities as a result of your physical health?** *[READ RESPONSE CHOICES]*

*(Circle one number)*

- All of the time ..... 1
- Most of the time ..... 2
- Some of the time ..... 3
- A little of the time ..... 4
- or None of the time..... 5

4b. **During the past four weeks, how much of the time have you accomplished less than you would like as a result of your physical health?** *[READ RESPONSE CHOICES]*

*(Circle one number)*

- All of the time ..... 1
- Most of the time ..... 2
- Some of the time ..... 3
- A little of the time ..... 4
- or None of the time..... 5

4c. **During the past four weeks, how much of the time were you limited in the kind of work or other regular daily activities you do as a result of your physical health?**  
*[READ RESPONSE CHOICES]*

*(Circle one number)*

- All of the time ..... 1
- Most of the time ..... 2
- Some of the time ..... 3
- A little of the time ..... 4
- or None of the time..... 5

4d. **During the past four weeks, how much of the time have you had difficulty performing work or other regular daily activities as a result of your physical health, for example, it took extra effort?** *[READ RESPONSE CHOICES]*

*(Circle one number)*

- All of the time ..... 1
- Most of the time ..... 2
- Some of the time ..... 3
- A little of the time ..... 4
- or None of the time..... 5

**The following three questions ask about your emotions and your daily activities.**

5a. **During the past four weeks, how much of the time have you had to cut down the amount of time you spent on work or regular daily activities as a result of any emotional problems, such as feeling depressed or anxious?** *[READ RESPONSE CHOICES]*

*(Circle one number)*

- All of the time ..... 1
- Most of the time ..... 2
- Some of the time ..... 3
- A little of the time ..... 4
- or None of the time..... 5

5b. **During the past four weeks, how much of the time have you accomplished less than you would like as a result of any emotional problems, such as feeling depressed or anxious?** *[READ RESPONSE CHOICES]*  
*(Circle one number)*

- All of the time ..... 1
- Most of the time ..... 2
- Some of the time ..... 3
- A little of the time ..... 4
- or None of the time..... 5

5c. **During the past four weeks, how much of the time did you do work or other regular daily activities less carefully than usual as a result of any emotional problems, such as feeling depressed or anxious?** *[READ RESPONSE CHOICES]*  
*(Circle one number)*

- All of the time ..... 1
- Most of the time ..... 2
- Some of the time ..... 3
- A little of the time ..... 4
- or None of the time..... 5

6. **During the past four weeks, to what extent has your physical health or emotional problems interfered with your normal social activities with family, friends, neighbors, or groups? Has it interfered . . .** *[READ RESPONSE CHOICES]*  
*(Circle one number)*

- Not at all ..... 1
- Slightly ..... 2
- Moderately ..... 3
- Quite a bit ..... 4
- or Extremely ..... 5

7. **During the past four weeks, how much did pain interfere with your normal work, including both work outside the home and housework? Did it interfere . . .** *[READ RESPONSE CHOICES]*  
*(Circle one number)*

- Not at all ..... 1
- A little bit ..... 2
- Moderately ..... 3
- Quite a bit ..... 4
- or Extremely ..... 5

8. **How much bodily pain have you had during the past four weeks? Have you had . .**  
*[READ RESPONSE CHOICES]*

*(Circle one number)*

- None..... 1
- Very mild..... 2
- Mild..... 3
- Moderate..... 4
- Severe..... 5
- or Very severe ..... 6

